2.8 Analysis

Factor analysis of the SAQ A trial principal axis factor analysis with scree plot will be calculated. On the basis of factor loadings on the first factor, it will be decided whether it is legitimate to provide an overall score for the questionnaire. Using the scree plot to determine factor number, an oblique rotation will be carried out and interpretation of emerging factor loadings (from the pattern matrix) determined.

Correlations between questionnaires

Correlations between questionnaires will be calculated using Pearson Correlations.

Discriminant validity We will test for significant differences between the SAQ and other scales using a mixed design analysis of variance (one within and one between) where groups are defined in two ways (a) maintenance dose oral corticosteroids and (b) cumulative dose oral corticosteroids. The aim of this analysis is to investigate whether the SAQ has better discriminant validity than other scales. First the interaction term of the analysis of variance will be used to determine whether sensitivity differs across all groups. Second, because the SAQ is expected to be more sensitive to discrimination at the top end of prednisolone use, a mixed design analysis of variance will be conducted on the two highest doses of prednisolone only.

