3.4.3 Sample size calculation

Three types of analysis are planned. Sample size is based on analysis 2 (see below where the sample is divided into quartiles and we test whether there are significant differences between quartiles. Four groups of 25 patients will detect an effect size of 0.3 with a power of 70% at a significance level 5%. The total sample is therefore 100 participants. The addition of a fifth site with the aim of also recruiting 25 patients will mean this analysis remains sufficiently powered even if one of the other sites under-recruits.

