3.6 Analysis

The SAQ provides two scores, the SAQ score which is the mean of all 16 domain specific items, and the SAQ-global score which is a single item score based on the SAQ-Global, which itself is based on a Borg scale [21]. Borg scales use multiple quantifiers at empirically derived points along the scale with the aim of achieving a ratio scale. In this analysis plan, the term SAQ will refer to both the SAQ score and the SAQ global score. Separate analyses will be carried out on the SAQ score and SAQ-global. Several analyses will be carried to ensure that the MCID concept is fit for purpose.

Data from 4, 8, 12 and 16 weeks will be compared to the data collected at week 0 (baseline), providing 4 change scores per patient. Patients can indicate any one of 5 levels of improvement in any of the four weeks, or, if there is no change or deterioration, up to 11 types of change. If patients report the same level of global rating of change at each of the four time points (e.g., they record 'a little better' at week 4 and 'a little better at week 8), the average SAQ change score will be calculated for that patient. This average will then be used as the SAQ change for that particular level of global rating of change. This procedure is followed so that each patient can contribute just one value to the population average of the SAQ change score at any level of global change, and which, in the case of the level of 'a little better' is used to calculate the MCID. We shall carry out three analyses to check on the validity of the MCID concept. If the checks come out positive, then the existing method of calculating the MCID (i.e., as the change in the SAQ that maps on to the global rating of change criterion of 'a little better) will be adopted.

If the checks are negative – i.e., suggesting some revision to the way the MCID concept is employed – then we will adapt the methodology in accordance with our findings.

What degree of change on the SAQ is associated with each of the 5 levels of improvement and 5 levels of deterioration on the global rating of change score?

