The mean, confidence intervals, and standard deviation of change of the SAQ will be calculated for each level of change in the GRCQ. These means will then be plotted (change in SAQ on x axis, global change on y axis) to show the relationship between change and perceived change at different degrees of change. These results should show that the change in the SAQ increases with increase in global change scores, and will be tested for by analysis of variance. This analysis is needed to show that the MCID is specific to the level of change of 'a little better' or 'a little worse' rather than any other level of global rating of change. The analysis will also check whether 'a little better' is equivalent in terms of 'a little worse' in terms of SAQ change.

Is the MCID transitive – i.e., is the MCID independent of level of deficit of quality of life?

Patients will be allocated to quartiles based on severity of the SAQ score at week 0. The mean, confidence intervals and standard deviation of change scores for change at 'a little better' will be calculated. Analysis of variance will be calculated for the four quartiles to test of transitivity. Effect size (eta) will be calculated. This analysis is needed to show that the MCID level can be applied across the full range of deficit of quality of life.

Are items in the SAQ equivalent with regard to the MCID – i.e., is change in all the 16 SAQ items equivalent in terms of their relationship with the global rating of change?

To test for equivalence, change in each of the 16 items of the SAQ and the SAQ-global will be correlated against the global rating of change score. These correlations will be examined and interpreted. Regression will be explored, but may be ruled out due to co-linearity. This analysis is needed to show whether weighting of items is needed when calculating the MCID, or whether the MCID is based simply on the mean of all items.

Demographic information analyses

In addition, we will also test whether baseline characteristics are similar across the four quartile groups and investigate whether the change in SAQ is related to the collected demographic and clinical data.

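### The analysis of variance across rating-of-change levels has no patient term, although one patient can supply values at up to four levels, so its standard errors for differences between levels are too large and the check loses some power

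*Protocol*

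**What the plan says.** Protocol section 3.6 compares weeks 4, 8, 12 and 16 with week 0, "providing 4 change scores per patient". Where a patient gives the same global rating at more than one visit, "the average SAQ change score will be calculated for that patient". The stated reason is that "each patient can contribute just one value to the population average of the SAQ change score at any level of global change".

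The first of the three checks then describes SAQ change at each rating level by mean, confidence interval and standard deviation. It expects that the "change in the SAQ increases with increase in global change scores, and will be tested for by analysis of variance". On purpose, the section says: "This analysis is needed to show that the MCID is specific to the level of change of 'a little better' or 'a little worse", as opposed to other ratings. The same check is to compare 'a little better' with 'a little worse'.

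No patient, within-subject or random term is named for this test. In section 2.8, where the protocol does intend a within-subject factor, it says so: "mixed design analysis of variance (one within and one between", for comparing the SAQ with other scales.

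**The concern.** The averaging rule removes dependence within a rating level but not between levels. A patient who reports 'a little better' at week 4 and something stronger at weeks 8 to 16 appears in at least two groups. Those values share one week 0 score and one patient's tendency to respond, so they are positively correlated. An ordinary analysis of variance takes the groups as independent and leaves that covariance out.

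At stake is the sensitivity of the check meant to show that SAQ change rises with the rating and that the MCID belongs to 'a little better' rather than to a nearby level. Ratings can spread over 11 levels, so some groups may be small, and no power is stated for this test.

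**Working it through.** **The plan's own figure.** Section 3.4.3 says "Sample size is based on analysis 2", the quartile comparison. With 4 groups of 25, effect size 0.3 read as Cohen's f and a 5% level, the noncentrality is 100 × 0.3² = 9 on 3 and 96 degrees of freedom. Power is 69.2%, which agrees with the stated 70%. It does not cover the test across rating levels.

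**Inputs.** From section 3.6: four change scores per patient, one shared baseline, at most one value per patient per level. Assumed, because the protocol does not give them: the within-patient correlation ρ, how often patients change level, and the slope of SAQ change on rating.

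**Two levels, by formula.** Let each level have n values with standard deviation s, and let a fraction w of patients appear in both.

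- True variance of the difference: (2s²/n)(1 − ρw)
- Variance used by ordinary ANOVA: 2s²/n
- Ratio of standard errors, ordinary to true: 1/√(1 − ρw)

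Example with ρ = 0.5, w = 0.5: 1/√0.75 = 1.15. With n = 25 and an assumed true difference of 0.5 SD, the ordinary standard error is √(2/25) = 0.283 SD and the true one is 0.283 × √0.75 = 0.245 SD. Power is then 0.41 with the ordinary standard error and 0.53 with the correct one.

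| ρ | w | SE ratio | Type I error, ordinary | Power, ordinary | Power, correct SE |
|---|---|---|---|---|---|
| 0 | any | 1.00 | 0.050 | 0.42 | 0.42 |
| 0.3 | 0.5 | 1.08 | 0.034 | 0.42 | 0.48 |
| 0.5 | 0.5 | 1.15 | 0.024 | 0.41 | 0.53 |
| 0.7 | 0.5 | 1.24 | 0.015 | 0.41 | 0.59 |
| 0.3 | 1 | 1.20 | 0.019 | 0.41 | 0.56 |
| 0.5 | 1 | 1.41 | 0.006 | 0.39 | 0.71 |
| 0.7 | 1 | 1.83 | 0.0003 | 0.36 | 0.90 |

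Full overlap (w = 1) is an extreme case.

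**Neighbouring levels, by simulation.** 100 patients, four visits, ratings drifting upward, the protocol's averaging rule, no true difference between levels:

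| Levels per patient | ρ | SE ratio | Overall test rejects (nominal 5%) |
|---|---|---|---|
| 2.8 | 0.3 | 1.16 | 3.4% |
| 2.8 | 0.5 | 1.25 | 2.7% |
| 2.8 | 0.7 | 1.41 | 2.1% |
| 2.8 | 0.8 | 1.48 | 1.7% |
| 1.6 | 0.3 | 1.11 | 5.1% |
| 1.6 | 0.5 | 1.18 | 3.8% |
| 1.6 | 0.7 | 1.21 | 3.0% |

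**Overall test, by simulation.** Six levels, an assumed slope of 0.12 SD per level, 1,000 runs per setting. Each cell gives the power of ordinary ANOVA, then of a model with a patient random effect applied to the same averaged values:

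| ρ | 1.8 levels per patient | 2.4 | 2.9 |
|---|---|---|---|
| 0.3 | 0.39, 0.42 | 0.47, 0.54 | 0.57, 0.70 |
| 0.5 | 0.32, 0.37 | 0.38, 0.56 | 0.52, 0.85 |
| 0.7 | 0.28, 0.44 | 0.36, 0.75 | 0.47, 0.97 |

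Under no difference the ordinary test rejected 1.4% to 3.9% of the time at ρ of 0.3 to 0.7. Two cautions apply to this table. The random-effect model was given the true variances, which flatters it. It also weights each average by the number of visits behind it. At ρ = 0 that weighting alone gave 0.63 to 0.64 against 0.48 to 0.62, so not all of each gap comes from the missing patient term.

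**The case against.** **The protocol never says the values are independent.** It says only analysis of variance, and a statistical analysis plan that is not shown could add a patient effect. That is fair as a limit on certainty. But section 3.6 does set out how repeated scores are handled (average within level, then compare levels), and that handling deals with only half of the dependence. Section 2.8 names a within factor where one is meant. The plain reading is an ordinary analysis of variance.

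**The overall test may have power to spare.** In a further simulation of ordinary ANOVA (2.8 levels per patient, ρ of 0.3 to 0.8), power was 97% to 99% at 0.20 SD per level and at least 99% at 0.25. If the SAQ tracks the rating well, the overall test will succeed anyway. This stands. The loss matters when the relation is weak, and more for comparisons between particular levels than for the overall test.

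**The consequence is not spelled out.** A reader might infer that failing to separate neighbouring levels would by itself force a change of MCID method. The protocol does not support that. It names no neighbouring-level contrast and sets no threshold for a negative result. It says only that the method will be adapted if the checks are negative, and its two examples of modification refer to the second and third checks. Comparing neighbouring levels follows from the stated purpose of specificity, but it is not a prescribed test.

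**Conclusion.** The point holds as a modest flaw in the stated method. On a plain reading, the standard errors for differences between neighbouring levels are about 1.1 to 1.5 times too large, for ρ of 0.3 to 0.8 and about 1.6 to 2.8 levels per patient. The effect is close to nil if ρ is near zero or few patients change level. All of these settings are assumptions.

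Two stronger readings should be resisted.

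- A reader might infer that the MCID or its confidence interval is wrong. Within a level each patient counts once, so each level's mean and interval, including those for 'a little better', are not affected by dependence between levels.
- A reader might infer too many false positives. For differences between levels the ignored covariance makes the test conservative. One simulation at ρ = 0 did reject 7% to 9% of the time, which was attributed to pooling averages of one to four visits; another gave about 5%. Neither figure comes from the dependence described here.

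**What to change.** In the first check of section 3.6, replace the analysis of variance with a linear mixed model for SAQ change, with rating level as a fixed factor and a random patient effect, or use patient-clustered standard errors. It can be fitted to the same averaged values, with weights for the number of visits averaged. Take from it a trend contrast, which matches the stated expectation that change increases with the rating, and the between-level differences, including 'a little better' against 'a little worse'. If those two are compared in size with the sign of one reversed, the contrast becomes a sum and the covariance acts in the opposite direction; the model handles either case.

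Keep the averaging rule, and keep the simple mean at 'a little better' as the MCID. Level means from the model weight patients differently and borrow across levels, so they should not replace the average that section 3.6 defines.

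The cost is a change of wording and slightly more analysis work. No new data, visits or patients are needed.

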3.3 Study outcome measures

3.3.1 Investigation questionnaires:

1. Severe Asthma Questionnaire (SAQ) (Appendix 2)
2. Global Rating of Change Questionnaire (Appendix 10)

This scale will be used by participants to indicate how much better they feel since commencing a biologic treatment for asthma. The 11-point scale ranges from -5 (a great deal worse) to 5 (A great deal better) [20].
3. EQ-5D-5L (Appendix 3)

3.3.2 Clinic Data to be collected:

Baseline characteristics:

Age

Sex

Spirometry: absolute FEV1 (litres) and percentage of predicted FEV1 (FEV1 %)

Forced Vital Capacity (FVC) (litres)

Body Mass Index (BMI)

Asthma severity: Treatment level by drug class classified by GINA step
Maintenance OCS dose (mg/day)Health care utilisation:
Emergency Department attendance in the last 12 months
Hospital admissions in the last 12 months

Clinic Data Outcome Measures to be recorded at each treatment visit:

Weight (Kg)
Maintenance OCS dose (mg/day)
Number of exacerbations since last clinic visit requiring OCS Health care utilisation, the number of:
Emergency Department attendances since last clinic visit
Hospital admissions since last clinic visit.

Must be recorded on the follow-up CRF at the final study visit (16 weeks), (weeks 4, 8 and 12 are optional):

FEV1 (litres)
FEV1 (% predicted)

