If the above show no problems with the existing methodology, then the MCID will be calculated from the average SAQ change for the rating of 'a little better'. That is, any patient who has provided a global rating of change of 'little better' will contribute an initial and final SAQ score to produce a SAQ difference score for each patient, and the average of the SAQ difference scores across patients will be then form the MCID. If there are problems, then we shall modify the MCID, for example, having different values for different levels of quality of life deficit (see 2 above) or by using a weighting of items (see 3 above).

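### The transitivity check groups patients by week-0 SAQ and compares change from that same score, so regression to the mean can create a severity gradient even if the MCID is constant

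*Protocol*

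**What the plan says.** Section 3.6 of the protocol defines the change score first: "Data from 4, 8, 12 and 16 weeks will be compared to the data collected at week 0 (baseline"), which gives up to four change scores per patient. If a patient gives the same rating at several visits, those changes are averaged, so each patient contributes one value per rating level.

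The second analysis in that section asks whether the MCID is independent of the level of deficit. "Patients will be allocated to quartiles based on severity of the SAQ score at week 0". The mean, confidence interval and SD of change at 'a little better' are then reported by quartile. "Analysis of variance will be calculated for the four quartiles to test of transitivity". "Effect size (eta) will be calculated". The stated purpose is to show that one MCID serves the full range of deficit.

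The end of section 3.6 says what may follow: "If there are problems, then we shall modify the MCID, for example, having different values for different levels of quality of life deficit".

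Section 3.3.1 describes the change rating: "This scale will be used by participants to indicate how much better they feel since commencing a biologic treatment for asthma". Section 3.4.3 sizes the study on this quartile comparison: "The total sample is therefore 100 participants". The protocol does not mention regression to the mean, the reliability of the week-0 score, or a correction for either.

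**The concern.** One observed week-0 score both places the patient in a quartile and is subtracted to form the outcome. A patient whose week-0 score is too low by chance is more likely to fall in the worst quartile, and the recorded change is too large by the same amount. The reverse happens in the best quartile. The artefact has the same form as the effect the analysis is meant to detect, a change at 'a little better' that varies with baseline deficit.

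Averaging over visits does not help, because all of a patient's changes share one week-0 score. The quartile means and eta are reported whether or not the ANOVA is significant. If severity-specific MCIDs were read from this table, they could be partly artefact: too large for the worst patients and too small for the best.

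**Working it through.** **The plan's own figure.** Four groups of 25, effect size 0.3 (read as Cohen's f), 5% level. The noncentrality is 100 × 0.3² = 9 with 3 and 96 degrees of freedom, which gives power of 69.2% against the stated 70%. The sample-size figure is not in error.

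**Inputs.** The grouping, the outcome, the four visits and the 100 participants come from sections 3.4.3 and 3.6. Everything else is assumed: SAQ reliability R of 0.95, 0.90, 0.85 or 0.80; true change with mean 0.5 and SD 0.4 in baseline-SD units, independent of baseline; rating noise SD 0.3; and about 22% giving 'a little better' at any one visit.

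**Formula when the rating reflects none of the week-0 error.** Scale the week-0 score to SD 1, so its error variance is 1 − R. With no true dependence on baseline, expected change falls by (1 − R) for each SD of better week-0 score. The means of the outer quartiles of a standard normal are ±1.2711, so

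spurious gap = 2 × 1.2711 × (1 − R) = 2.542 × (1 − R).

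- R = 0.95: 2.542 × 0.05 = 0.13 SD
- R = 0.90: 2.542 × 0.10 = 0.25 SD
- R = 0.85: 2.542 × 0.15 = 0.38 SD
- R = 0.80: 2.542 × 0.20 = 0.51 SD

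Suppose the true change is 0.50 SD in every quartile. At R = 0.90 the worst quartile shows 0.50 + 0.127 = 0.63 and the best 0.50 − 0.127 = 0.37, a ratio of about 1.7. At R = 0.80 the values are 0.75 and 0.25, a ratio of about 3.

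**Simulation with selection on the rating** (100 enrolled, one follow-up, about 22 rating 'a little better', quartiles cut on all 100). Each cell gives the gap in baseline SD and the false rejection rate of the 5% ANOVA, by the share of week-0 error variance that the rating reflects:

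| R | none reflected | half reflected | 80% reflected |
|---|---|---|---|
| 0.95 | 0.12; 6% | 0.09; 6% | 0.05; 5% |
| 0.90 | 0.25; 9% | 0.17; 7% | 0.10; 6% |
| 0.85 | 0.38; 11% | 0.23; 9% | 0.15; 6% |
| 0.80 | 0.50; 14% | 0.32; 11% | 0.18; 8% |

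Repeat runs move the gaps by 0.01 to 0.02 SD, so the working ranges are about 0.13 to 0.50 with none reflected and about 0.05 to 0.19 with 80% reflected.

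**Dependence on the number of contributors** (none reflected, R from 0.95 down to 0.80). The protocol counts a patient who gives the rating at any of four visits.

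- About 22 contributors (one visit): 6–14% false rejection.
- About 60 contributors (100 enrolled, four visits, the protocol's averaging): about 9–43%.
- 25 in every quartile, as in section 3.4.3: 11–60% with true-change SD 0.3, or 8–46% with SD 0.5.

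**Eta.** With 20 contributors, mean eta is 0.38 to 0.43 against 0.37 without the artefact. With 32 it is 0.30 to 0.36 against 0.29. With 25 per quartile and true-change SD 0.3 it is 0.19 to 0.30 against 0.16. At small counts most of the inflation is ordinary small-sample bias.

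**The case against.** The strongest case against is that the harm is conditional three times over. The week-0 score must carry appreciable error, and the protocol gives no reliability. The rating must miss that error, yet patients rate change since starting treatment, so a genuinely bad spell at week 0 may be partly built into the rating. And the team must choose to split the MCID, which section 3.6 offers only as an example. All of this stands. It limits the size, and the table shows that a gap remains even at 80% reflected. The bias essentially disappears only if the week-0 score has no error or the rating carries that error too.

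Section 3.6 also plans to relate SAQ change to demographic and clinical data that lie outside the SAQ. That mitigates in part. It is not confined to 'a little better' and is not tied to the MCID decision.

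Four other readings are tempting and go too far:

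- A reader might infer that the MCID itself is biased. The overall value averages all 'a little better' patients and does not use the quartiles.
- A reader might infer that the ANOVA seldom rejects falsely, or that it usually does. Neither can be fixed from the protocol, because the rate depends on how many patients ever give that rating. Section 3.2 also speaks of 30 to 50 per site at five sites (150 to 250) against the 100 in section 3.4.3.
- A reader might infer that any observed gradient is pure artefact. A real one could exist, and one in the opposite direction could be masked.
- A reader might see a second defect for SAQ-global, since "In this analysis plan, the term SAQ will refer to both the SAQ score and the SAQ global score". But section 3.6 defines the SAQ score as the 16-item mean and uses that term for the quartiles, so this is a side matter of wording.

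**Conclusion.** The concern holds as a directional bias in an analysis that the protocol fixes; it is not a detail left to a later plan. Over assumed reliabilities of 0.95 to 0.80, the spurious worst-to-best gap is about 0.13 to 0.50 baseline SD if the rating reflects none of the week-0 error, and about 0.05 to 0.19 SD if it reflects 80%. False rejection with none reflected is about 6–14% with 22 contributors, about 9–43% with about 60, and higher with more. Eta is inflated too, modestly at small counts.

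The direction needs only imperfect reliability and a rating that does not fully carry week-0 error. The sizes rest on assumed inputs and are a range, not an estimate. The consequence is confined to the quartile results and to any severity-specific MCIDs drawn from them. It should be corrected before analysis, because the change is cheap and the protocol names such a split as a possible response.

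**What to change.** 1. Keep the week-0 SAQ quartile table, label it as subject to regression to the mean, and state that severity-specific MCIDs will not be taken from it alone.
2. Add, as a sensitivity analysis, the same 'a little better' comparison with patients grouped on week-0 EQ-5D-5L, which section 3.5 already requests at first treatment, or on another week-0 measure outside the change score. Report estimates and confidence intervals.
3. Add a reliability-based correction over a stated range of reliabilities. It will over-correct where the rating reflects week-0 fluctuation, so it too is a sensitivity analysis.
4. Use these results to inform interpretation, not as a pass/fail gate.

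The cost is wording and a little more analysis, with no new data. The regrouping has limits. EQ-5D-5L ranks a related but different deficit and may share some week-0 error. Assuming a true-score correlation of 0.7 with the SAQ and an EQ-5D-5L reliability of 0.8, independent errors bring the spurious gap to about 0 and rejection to 4–6%. If 30% of week-0 error variance is shared, there is no gain at SAQ reliability 0.95 (0.13 against 0.12 SD), while at 0.80 the gap falls from 0.50 to 0.27 SD. Power is low: at an assumed SAQ reliability of 0.90, a real 0.5 SD gradient would show as about 0.2 to 0.4 SD (true-score correlation 0.5 to 0.9) and be significant only 6–15% of the time with 20 to 32 patients. A flat result there does not prove that one MCID fits all, which is why it should not serve as a gate.

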3.2 Study Design

Type of study: A multi-centre sensitivity to change study, using the SAQ, other questionnaire measures and clinic data

Duration of the study: 18 months.

Sample size: Between 30 and 50 participants per each of the five participating sites:

1. University Hospitals Plymouth, NHS Foundation Trust, Plymouth, UK
2. Royal Brompton and Harefield NHS Foundation Trust, London, UK
3. University Hospital of South Manchester, Manchester University NHS Foundation Trust, UK
4. Birmingham Heartlands Hospital NHS Foundation Trust, Birmingham, UK
5. Royal Devon and Exeter Hospital NHS Foundation Trust, Exeter, UK

Baseline questionnaire data from participants recruited for this part of the study will be added to the dataset for part 1.

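### The transitivity check reports unadjusted eta, which is biased upward and can overstate how far the MCID depends on baseline deficit; the F test itself is not affected

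*Protocol*

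**What the plan says.** Protocol section 3.6, second analysis, splits patients into quartiles of week-0 SAQ score and looks at change scores at the rating *a little better*. It plans means, confidence intervals and standard deviations of those change scores, and then: "Analysis of variance will be calculated for the four quartiles to test of transitivity. Effect size (eta) will be calculated". It gives no bias adjustment and no interval for eta.

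Section 3.4.3 sizes the study on this analysis: "Four groups of 25 patients will detect an effect size of 0.3 with a power of 70% at a significance level 5" per cent. It does not name the effect-size metric. It concludes: "The total sample is therefore 100 participants".

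The end of section 3.6 says what may follow if the checks reveal problems. One option is "having different values for different levels of quality of life deficit". No threshold of eta, or of anything else, is set for taking that option.

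**The concern.** Eta is the square root of the between-group share of the total sum of squares. Sample means differ by chance even when the true means are equal, so eta is almost always above zero, and more so the fewer the patients. The analysis uses only patients who gave one particular rating on an 11-point scale, so the number analysed may be well below enrolment.

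An eta of sizeable appearance could then be reported when the MCID does not depend on baseline deficit at all. The planned 0.3 is also on an unnamed scale, so a reader is likely to set the observed eta directly against it. At stake is how the result is read when the investigators decide between one MCID and several.

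**Working it through.** **Inputs.** From section 3.4.3: four groups of 25 (N = 100), effect size 0.3, power 70%, significance level 5%. From section 3.6: one-way analysis of variance over four quartiles, at most one value per patient at a given rating. The number n of patients at *a little better* is not given; 20 to 125 is assumed below. Normal errors with equal variance are assumed.

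**1. The plan's own figure.** Power comes from the noncentral F distribution with 3 and 96 degrees of freedom and noncentrality N × f². With f = 0.3 this is 100 × 0.09 = 9, and power is 69.2%, which agrees with the stated 70%. Other readings of 0.3 fit less well:

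- eta = 0.3, so f = 0.3/√(1 − 0.09) = 0.314: power 73.7%
- eta-squared = 0.3 or f-squared = 0.3: power above 99%
- standardised difference of 0.3 between two groups of 25: power 18%

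So 0.3 is best read as Cohen's f. On the other scales it is eta-squared = 0.09/1.09 = 0.083 and eta = 0.3/√1.09 = 0.287.

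**2. Eta when the MCID is constant.** With equal true means, eta-squared follows a Beta(3/2, (n − 4)/2) distribution. Its mean is 3/(n − 1). The mean of eta is B(2, (n − 4)/2) / B(3/2, (n − 4)/2), where B is the beta function.

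| n (assumed) | Mean eta-squared | Mean eta | Chance that eta exceeds 0.287 |
|---|---|---|---|
| 20 | 0.158 | 0.37 | 70% |
| 30 | 0.103 | 0.30 | 52% |
| 40 | 0.077 | 0.26 | 37% |
| 50 | 0.061 | 0.23 | 26% |
| 75 | 0.041 | 0.19 | 10% |
| 100 | 0.030 | 0.16 | 4% |
| 125 | 0.024 | 0.14 | 1.5% |

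Unequal groups change nothing of note: a simulation with 4, 6, 8 and 12 patients (n = 30) gives a mean eta of 0.299.

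**3. Eta when the planned effect is real.** With f = 0.3 the true eta is 0.287. The simulated mean of sample eta is 0.32 at n = 100 and 0.40 at n = 30.

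**4. The corrected measures.** In the same simulations, omega-squared and epsilon-squared average 0.00 under equal means at both n. With f = 0.3 (true value 0.083), omega-squared averages 0.081 at n = 100 and 0.078 at n = 30; epsilon-squared averages 0.082 and 0.080.

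**5. What the F test shows beside eta.** Take n = 30 and an observed eta of 0.30. Then F = (0.09/3) / (0.91/26) = 0.030/0.035 = 0.86 on 3 and 26 degrees of freedom, with p = 0.48. The test is not misled. But its power for f = 0.3 at n = 30 is only 21.9%, so a non-significant result there says little about constancy.

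**The case against.** The strongest reply is that eta decides nothing. Transitivity is tested by the analysis of variance, whose F test already allows for the null distribution of eta, so the type I error stays at 5% whatever n is. An eta of 0.30 from 30 patients would stand beside p = 0.48. This is right. A reader might infer that the bias will cause the MCID to be split wrongly by severity. The documents do not support that: no eta threshold is set, and the harm would require someone to overlook the planned test.

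A reader might also take eta to be the only measure of the dependence. It is not. The same paragraph plans means with confidence intervals straight after forming the quartiles. Read in place, these show the variation by quartile in SAQ units.

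Third, it is tempting to say that about 30 patients will be analysed and that the null eta then equals the planned effect. The figure of 30 is not in the protocol. Section 3.4.3 plans 100. Section 3.2 gives "Between 30 and 50 participants per each of the five participating sites", that is 150 to 250 in all, and each patient has four occasions to give the rating. At n = 100 the bias is modest. The equality also mixes two scales, since the planned 0.3 corresponds to eta 0.287, though a gap of 0.013 matters little in practice.

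Finally, eta is a standard descriptive statistic, and the choice of interval could be left to a statistical analysis plan. That carries some weight. But the protocol names this statistic itself, so the choice is open to comment.

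What remains is that the stated effect size is biased in a known direction, most of all when n is small. That is also where the F test is weakest and a reader is most likely to turn to the effect size.

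**Conclusion.** The point holds as a minor one about reporting. Unadjusted eta overstates the dependence of the MCID on baseline deficit. Under a constant MCID the overstatement is 0.16 on average if 100 patients are analysed, 0.23 if 50 and 0.30 if 30. Its practical size therefore rests on the number rating *a little better*, which the protocol does not give. Neither the error rate of the test nor the quartile means are affected.

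If the subset proves small, the likelier mistake is the opposite of a false split: a non-significant F taken as proof that the MCID is constant. An interval for the effect size guards against both misreadings. That section 3.4.3 counts 100 patients while the test uses only those with one rating is a separate matter of power, which a change of effect-size measure does not repair.

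**What to change.** In section 3.6, second analysis, replace eta by omega-squared or epsilon-squared with a confidence interval from the noncentral F distribution. Report negative estimates as they fall, since setting them to zero would bring back an upward bias. Add that a non-significant F will be read together with this interval and not as evidence of a constant MCID.

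In section 3.4.3, state that 0.3 is Cohen's f, equal to eta 0.287 and eta-squared 0.083, so that planned and observed effects can be compared.

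The cost is a few sentences. The data and the analysis of variance stay the same, and the corrected measures follow from F and its degrees of freedom.
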